7.1.1 Risks associated with Clinical Investigation participation

Potential risks associated with the study MRI scan are the same as or comparable to those associated with MRI scans of an implanted medical device powered by a battery or other electrical source of power including, but not limited to, those listed in the Adverse Events and Adverse Device Effects section of the protocol.

7.2 Risk Control Measures

The risks associated with MRI scanning of subjects implanted with implantable active medical devices have been identified through clinical evaluation, including an exhaustive literature search.

Risks normally associated with ICDs and transvenous leads will be minimized in the study by selecting investigators who are experienced in treating subjects implanted with ICDs, evaluating implanted ICD systems, and who are trained in the Asia MRI ICD Study. Subjects will be actively monitored during the study scan using verbal communication, ECG, and continuous pulse oximetry monitoring. The investigator or other ACLS-certified personnel who have been trained on the study protocol will be present during the study MRI scan to address cases of asystole or hemodynamic collapse that may occur during the study MRI scan. In addition, because the study MRI scan is not meant to be diagnostic in nature, contrast agents will not be used, thereby eliminating the risk of allergic or adverse reactions to contrast agents.

Risks will also be minimized by careful assessment of each subject prior to enrollment. After enrollment, subjects in the study will be followed as specified in this CIP to monitor the condition of the implanted system and the battery after the subject has undergone the study MRI scan.

Clinical Investigation Plan

In order to safely perform an MRI scan on a subject with the implanted study system, the physician/clinician should do the following as stated in the MRI Ready Systems Manual: MRI Procedure Information for the St. Jude Medical™ MR Conditional System:

- Confirm that the patient has an MR Conditional System
- Confirm that no adverse conditions to MRI scanning are present (e.g. additional hardware)
- Review the potential adverse events
- Generate a report of the patient's permanently programmed parameters
- Select and Save MRI Settings
- Review the MRI Checklist and Program the MRI Settings using the Merlin® PCS
- Subject receives the MRI Scan
- Disable MRI Settings Using the Merlin® PCS

After the MRI scan and at the 1 Month Post Scan visit, the ICD will be interrogated to verify appropriate ICD function, to evaluate pacing and sensing characteristics, and to assess any adverse events.

Overall, the clinical study design, subject selection process, and procedures developed for scanning and monitoring of the subject during the MRI scan have all been designed to minimize risks to the subject.

While steps have been taken to identify and reduce or minimize risks associated with the study MRI scan and participation in the study, there may be risks that are unknown at this time.

7.3 Possible interactions with concomitant treatments

Other than the study MRI scans, there are no treatments that the subject would not otherwise receive as part of the subject's medical management related to having an implanted ICD system. While an MRI scan is not part of the usual treatment regimen for subjects implanted with an ICD, it is an accepted imaging modality used in the diagnosis of diseases or other medical condition.

The MRI scanner, methods used to scan the subject (scan sequences), and monitoring procedures in and of themselves are not investigational. As such, there are no anticipated interactions with concomitant medical treatments or concurrent medical interventions associated with the study MRI scan.

The device checks at each study visit are standard of care, or involve testing of the device and lead that are normally done at a routine device check. As such, there are no anticipated interactions with concomitant medical treatments or concurrent medical interventions associated with the study visits.

**Clinical Investigation Plan****7.4 Anticipated Benefits**

The information collected in this clinical investigation will provide further understanding the effects of Thoracic MRI scans on ICDs. Individual subjects will not receive any direct benefit as a result of their participation in this investigation.

8 Requirements for Investigator records and reports**8.1 Deviations from CIP**

A deviation is defined as an event where the clinical investigator, site personnel, Sponsor or Sponsor representative did not conduct the clinical investigation according to the CIP. The investigator is not allowed to deviate from the CIP, except as specified under emergency circumstances to protect the rights, safety and well-being of the subject.

Regulations require Investigators obtain approval from the Sponsor and the IRB/EC (if required) before initiating changes in or deviations from the CIP. The Principal Investigator may call or email and discuss the potential deviation with the Sponsor. Deviation to the CIP necessary to protect the life or physical well-being of a subject shall be documented and reported to the Sponsor and the IRB/EC as soon as possible, but no later than 5 working days.

In some cases, failure to comply with the CIP may be considered failure to protect the rights, safety and well-being of subjects, since the non-compliance exposes subjects to unreasonable risks. For example, failure to adhere to the inclusion/exclusion criteria, failure to perform safety assessments intended to detect adverse events. Investigators should seek minimization of such risks by adhering to the CIP.

Regulations require that the PI maintain accurate, complete, and current records, including documents showing the date of and reason for every deviation from the CIP. Relevant information for each deviation will be documented as soon as possible on the appropriate CRF. The site will submit the CRF to the Sponsor.

8.2 Safety reporting

The safety reporting performed both by the investigator and Sponsor will start as soon as the study procedure begins. This is defined as from the time the subject enrolled under this clinical investigation date of signature of the informed consent – or definition of “enrolled” in the CIP).

**Clinical Investigation Plan**

The safety surveillance and the safety reporting will continue until the last investigational visit has been performed, the subject is deceased, the subject/investigator concludes his participation into the clinical investigation or the subject withdrawal from the clinical investigation.

All Adverse Device Effects (serious or non-serious) are to be documented and reported to the sponsor as soon as possible after becoming aware of the event.

Adverse Event (AE)

Any untoward medical occurrence, unintended disease or injury, or untoward clinical signs (including abnormal laboratory findings) in subjects, users or other persons, whether or not related to the investigational medical device under clinical investigation.

This definition includes events related to the investigational medical device or the comparator.

This definition includes events related to the procedures involved.

Serious Adverse Event (SAE)

An adverse event that led to:

- Death
- A serious deterioration in the health of the subject, that either resulted in:
 - A life-threatening illness or injury OR
 - A permanent impairment to a body structure or a body function OR
 - An in-patient or prolonged hospitalization OR
 - A medical or surgical intervention to prevent life-threatening illness or injury or permanent impairment to a body structure or a body function OR
- Fetal distress, fetal death or a congenital abnormality or birth defect

A planned hospitalization for a pre-existing condition, or a procedure required by the CIP is not considered a serious adverse event.

Adverse Device Effect (ADE)

An adverse event related to the use of an investigational medical device.

This definition includes adverse events resulting from insufficient or inadequate instructions for use, deployment, implantation, installation, or operation, or any malfunction of the investigational medical device.

This definition includes any event resulting from the use error or from intentional misuse of the investigational medical device.

Serious Adverse Device Effect (SADE)

Adverse device effect that has resulted in any of the consequences characteristic of a serious adverse event.

**Clinical Investigation Plan**

Additional information may be requested by the Sponsor in order to support the reporting of ADEs or SADEs to regulatory authorities as applicable.

NOTE: If an adverse device event is documented at the subject's last follow up visit, both the notification and follow-up information on the AE CRF are to be provided to the sponsor.

Adverse device events will be monitored until they are adequately resolved or the subject has ended his/her participation in the trial, whichever comes first. The status of the subject's condition should be documented at each visit.

For the purposes of this clinical investigation the following events will be reported: ADEs, SADEs and Death events.

Reportable events shall be submitted to the Sponsor. The Sponsor will ensure that all applicable events are reported to the relevant authorities as per regulations. The sites should notify the Sponsor of reportable adverse events by creating and saving the applicable case report form within the electronic data capture system. Additional information may be requested by the Sponsor in order to support the reporting of ADEs, SADEs and Deaths to regulatory authorities. The investigator must notify the IRB/EC, if appropriate, in accordance with national and local laws and regulations, of the ADEs or SADEs reported to the Sponsor.

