3.3.2 Descriptive Endpoints

- Demographics and medical/surgical history such as gender, age, history of smoking, cardiac disease history, arrhythmia history, and indication for ICD implant, etc.
- Proportion of SJM high voltage lead implanted with SJM MR Conditional ICD with capture threshold increase of $\leq 0.5V$ @ 0.5ms from pre-MRI scan testing to 1 month post-MRI scan testing
- Proportion of SJM high voltage lead implanted with SJM MR Conditional ICD with sensing amplitude decrease of $\leq 50\%$ from pre-MRI scan testing to 1 month post-MRI scan testing
- Average and Peak Specific Absorption Rate (SAR) during MRI scan, MRI visit duration in MRI laboratory and total MRI scan duration in MRI laboratory.
- Adverse events and death

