5.2 Descriptive Endpoints

- Demographics and medical/surgical history such as gender, age, history of smoking, cardiac disease history, arrhythmia history, and indication for ICD implant, etc. Continuous variables will be summarized as sample size, mean, standard deviation, minimum and maximum. For categorical variables, the counts and percentages of subjects will be summarized for each category.
- Proportion of SJM high voltage lead implanted with SJM MR Conditional ICD with capture threshold increase of $\leq 0.5V$ @ 0.5ms from pre-MRI scan testing to 1 month post-MRI scan testing.
This proportion will be calculated as number of subjects who had high voltage lead with

[REDACTED]

Clinical Investigation Plan

capture threshold increased of $\leq 0.5V$ @ 0.5ms from pre-MRI scan testing to 1 month post-MRI scan testing divided by total number of subjects who had high voltage lead implanted, undergo a MRI scan and with both pre-MRI scan and 1 months Post MRI scan capture threshold available.

- Proportion of SJM high voltage lead implanted with SJM MR Conditional ICD with sensing amplitude decrease of $\leq 50\%$ from pre-MRI scan testing to 1 month post-MRI scan testing. This proportion will be calculated as number of subjects who had high voltage lead with sensing amplitude decrease of $\leq 50\%$ from pre-MRI scan testing to 1 month post-MRI scan testing divided by total number of subjects who had high voltage lead implanted, undergo a MRI scan and with both pre-MRI scan and 1 months Post MRI scan sensing amplitude available.
- Average and Peak Specific Absorption Rate (SAR) during MRI scan, MRI visit duration in MRI laboratory and total MRI scan duration in MRI laboratory
Average and Peak Specific Absorption Rate (SAR) during MRI scan, MRI visit duration in MRI laboratory and total MRI scan duration in MRI laboratory will be summarized as mean, standard deviation, minimum, median and maximum.
- Adverse events and death
The number of events, number of subjects who encountered the events will be summarized for each event category for ADE and SADE separately. The number of death will be summarized as counts and percentages for each primary cause.

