5.9 Deviations from Statistical Plan

If any deviations from the original statistical plan occur, such deviations will be documented in the clinical study report or statistical report containing the analysis results.

6 Device(s) under investigation

The following market-released devices* will be used in this clinical investigation in an MRI environment according to MRI-conditional labeling.

Table- 4: Identification of Devices* under Investigation

Device name	Model/Type/Description	Manufacturer	Region/ Country	Investigational or Market Released
Ellipse VR	CD1377-36QC/ICD/Single Chamber	SJM	Outside US	Market Released
Ellipse VR	CD1377-36Q/ICD/Single Chamber	SJM	Outside US	Market Released
Ellipse DR	CD2377-36QC//ICD/Dual Chamber	SJM	Outside US	Market Released
Ellipse DR	CD2377-36Q/ICD/Dual Chamber	SJM	Outside US	Market Released
Durata	7120Q/Lead/Active fixation, dual shock, 17 cm spacing, DF4	SJM	Outside US	Market Released

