Potential Lead Related Events	
Refer to the lead user's manual for a full list of potential adverse events (Refer to Appendix-I) 
The high voltage leads are market released transvenous, steroid-eluting defibrillation leads. The adverse events associated with these leads are the same as those associated with other market-released transvenous defibrillation leads.
 
These risks are mitigated through the selection of investigators who are qualified by training and/or experience to evaluate and treat subjects implanted with an ICD system.

In addition, subjects may also experience unavoidable events related to the MRI scan. An unavoidable event is an event related to the MRI scan that is expected to occur for a projected duration in all subjects. Unavoidable events are not reportable unless the condition worsens or continues beyond the time frame listed below. Unavoidable events do not need to be reported on an adverse event form if they are resolved within the time frame specified. These events are expected to occur with any MRI scan, including the study MRI scans.

Clinical Investigation Plan

Table 6: Unavoidable events related to the MRI Scan

Event	Time Frame post – MRI scan
• Claustrophobia	• During MRI scan
• Mild diaphoresis	• During and < 1 hour post MRI scan
• Sensation of bodily warmth	• During and < 1 hour post MRI scan
• Sensation of warmth at device pocket not arising to the level of discomfort	• During and < 1 hour post MRI scan
• Hearing impairment	• < 24 hours
• Body stiffness related to immobility	• < 48 hours

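### Non-fatal harm from the study scan that does not involve the ICD is missing from the section 8.2 reportable list and the section 5.2 safety table, while the Table 6 rule makes some of it reportable

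*Combined protocol and SAP*

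**What the plan says.** The provisions are spread over several sections of the Clinical Investigation Plan.

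- **Section 8.2, reportable events:** "For the purposes of this clinical investigation the following events will be reported: ADEs, SADEs and Death events".
- **Section 8.2, definitions:** the adverse event definition is broad and says of itself "This definition includes events related to the procedures involved". The ADE definition is narrower: "An adverse event related to the use of an investigational medical device". A SADE is an ADE with a serious outcome.
- **Section 7.1, text before Table 6:** "Unavoidable events are not reportable unless the condition worsens or continues beyond the time frame listed below". Table 6 lists six effects. Its limits include under 24 hours for hearing impairment and under 48 hours for stiffness from lying still. The text says these effects can be expected with any MRI scan, and it refers to an adverse event form.
- **Section 3.3.2:** lists "Adverse events and death" as a descriptive endpoint.
- **Section 5.2:** under the same label, counts of events and of subjects "will be summarized for each event category for ADE and SADE separately", plus deaths by primary cause.
- **Section 6:** introduces Table 4 with "The following market-released devices* will be used in this clinical investigation in an MRI environment". The table names ICDs and leads only.
- **Section 7.3:** "The MRI scanner, methods used to scan the subject (scan sequences), and monitoring procedures in and of themselves are not investigational".

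**The concern.** The thoracic scan is the one procedure that subjects undergo solely because of the study. It is not diagnostic, and section 7.4 states that subjects gain no direct benefit. Non-fatal harm from it therefore belongs in the safety record whether or not the ICD is involved. The reporting list and the table are both built on device-relatedness, whereas the Table 6 rule is built on relation to the scan. Where the two bases differ, an event may go unreported, or be reported at one site and not at another. The descriptive safety summary for each phase would then depend partly on how sites read the protocol.

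**Working it through.** No figure in the documents tests this point, so the check is a comparison of text.

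**Step 1: which device must an ADE relate to?** Table 4 and its footnote cover ICD systems and leads. Section 7.3 says the scanner, sequences and monitoring are not themselves investigational. On that reading, an event caused only by the scan or its monitoring is an AE (the definition covers procedures) but not an ADE.

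**Step 2: follow typical non-fatal events through the plan.**

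| Event after the study scan | AE (8.2) | ADE (8.2) | On the 8.2 list | Table 6 rule (7.1) | Row in 5.2 |
|---|---|---|---|---|---|
| Lead heating with loss of capture | yes | yes | yes | not in Table 6 | yes |
| Burn at an ECG electrode, ICD not involved | yes | no | no | not in Table 6 | none |
| Hearing impairment beyond 24 hours | yes | unclear | only if called an ADE | reportable | only if called an ADE |
| Hearing impairment resolved within 24 hours | yes | unclear | only if called an ADE | exempt | none intended |

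The second row is the gap and the third is the contradiction. Only one of the six Table 6 items, warmth at the pocket, names the device, so the third row is not a rare special case.

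**Step 3: do the visit procedures close the gap?** Table 1 asks sites to evaluate ADEs and SADEs at each visit, and section 4.6.2 repeats this at one month. Section 4.7 defines an unscheduled visit by an ADE or SADE associated with the ICD system. The ethics-committee notice for events in 8.2 also names ADEs and SADEs. None of these adds a class for scan-only events.

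**Step 4: what is not touched?** Section 3.3.1 defines a complication as a type of SADE, and the endpoint requires relation to the ICD system. Scan-only events are outside it by design, so the test against 90% is unchanged. Section 8.2.1 requires every death to be reported.

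**Step 5: illustration of size.** The documents give no rate of non-fatal scan-only events, so the rates p below are assumptions. With n = 168, the number of completers at which each phase's dataset is frozen (section 5.6), the expected number is n × p and the chance of at least one is 1 − (1 − p)^n.

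| Assumed p | Expected number | Chance of at least one |
|---|---|---|
| 0.5% | 168 × 0.005 = 0.8 | 1 − 0.995^168 = 57% |
| 1% | 168 × 0.01 = 1.7 | 1 − 0.99^168 = 82% |
| 2% | 168 × 0.02 = 3.4 | 1 − 0.98^168 = 97% |
| 5% | 168 × 0.05 = 8.4 | 1 − 0.95^168 = over 99.9% |

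These are events that could occur, not events shown to be lost. How many would go uncounted depends on how sites class them.

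**The case against.** The strongest reply is that the plan can be read so that scan events are ADEs. Table 6 sits under a heading on anticipated adverse device effects. Section 7.1 calls the study scans investigational, in the sense of studying their effect on the implanted system. Section 4.6.1.3 speaks of ADEs and SADEs that the scan causes. A site reading it this way would report a Table 6 event past its limit as an ADE, and it would enter the table. This stands in part: it makes exclusion of those events uncertain. It does not settle the matter, because section 7.3 points the other way and the events named in 4.6.1.3 are clotting, pulmonary embolism and heating of the lead tip or pocket.

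It can also be said that other routes exist. Section 4.6.1.2 has changes and complaints during the scan recorded. If a scan is not tolerated, the subject is assessed for adverse events, and the sequence, scan duration and SAR level go to the sponsor. This is partial capture. It creates no reporting class or table row, and the intolerance provision does not reach harm that appears after a completed scan.

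Finally, the objective is ICD performance, the devices are market-released, and ADE/SADE collection runs consistently through Table 1, 4.7, 5.2 and 8.2. That is a fair account of a deliberate scope. It does not explain why section 7.1 makes scan effects reportable outside that scope.

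**Conclusion.** The point holds as a conflict between sections 8.2 and 5.2 on one side and the Table 6 rule in 7.1 on the other. It leaves a gap for non-fatal scan-only injuries that Table 6 does not list. The gap rests on reading the investigational device as the ICD system, which Table 4 and section 7.3 support. It is confined to the descriptive safety summary, and its size cannot be known from the documents.

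A reader might infer more, and the documents do not support it:

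- *That no scan-only harm reaches the sponsor.* Section 7.1 gives Table 6 events past their limit a reporting route, and all deaths are reported.
- *That an under-count is certain.* Some sites may class these events as ADEs. What can be shown is inconsistent classing and, for unlisted events, absence from the list.
- *That section 3.3.2 makes all adverse events reportable, or that its endpoint cannot be produced.* It is a short label with no reporting rule. Section 5.2 defines a table under that label, and the table can be built from the events 8.2 collects.
- *That the primary result is at risk.* It counts only device-related complications.

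The change is worth making because it is cheap and concerns harm from a procedure that the study itself imposes.

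**What to change.** Reconcile sections 5.2, 7.1 and 8.2.

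1. In 8.2, replace the reportable list with: *ADEs, SADEs, deaths, and any AE or SAE related to the MRI scan procedure, except Table 6 events that neither worsen nor exceed their stated time frame.* The exception matters: without it, the new wording would pull in the within-limit events that 7.1 exempts and expects in all subjects.
2. In 5.2, add a row group, by phase: *MRI-scan-procedure-related AE/SAE, not device-related.*
3. Bring the evaluation lines in Table 1 into line with the new list.

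The primary endpoint, its analysis and the sample size stay as they are. The cost is a few more AE forms and a slightly less favourable safety table. The AE case report form is not in the documents. If it has no field for relation to the scan procedure, one must be added.
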